3.1 To determine the safety and tolerability of oral valganciclovir as add-on therapy in patients with IPF tolerating standard treatment with pirfenidone. 30 individuals with a diagnosis of IPF and positive serology for EBV or CMV will be enrolled in this study at Vanderbilt University Medical Center and randomized to receive either valganciclovir or placebo in a 2:1 ratio for 12 weeks. The primary endpoint will be rate of discontinuation of study drug due to adverse events in subjects randomized to valganciclovir compared to placebo. In addition, we will compare type, frequency and duration of adverse events (AE) and serious adverse events (SAE) between valganciclovir and placebo subjects.

3.2 To investigate the effect of anti-herpesvirus treatment on changes in viral load and immune responses against herpesvirus. A subset of study subjects will undergo bronchoscopy with BAL at the time of study entry and at 12 weeks for measurement of: 1) immune response to herpesviruses in lung lymphocytes and 2) herpesvirus DNA in cell-free BAL fluid. Additional studies to investigate changes in the immune response in peripheral blood lymphocytes to herpesviruses will include: 1) analyzing PD-1 expression by T lymphocytes and 2) quantifying CD8+ T cell immune responses to herpesvirus antigens at study entry and after 12 weeks of therapy. These parameters will be reassessed at 6 months and 1 year after study entry

to determine whether changes in anti-herpesvirus immune responses persist or revert to pre-treatment levels, thus shedding light on the duration of therapy needed to potentially alter disease progression.

4. Endpoints

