4.1. Primary Endpoint

4.1.1. The primary outcome will be safety and tolerability will be determined by type, frequency and duration of adverse events (AE) and serious adverse events (SAE) in subjects receiving valganciclovir versus placebo.

4.2. **Secondary Endpoints:** We will evaluate for trends in other clinical endpoints, as well as viral and immune endpoints over time in the valganciclovir group compared to the placebo group.

4.2.1. We will determine the change in pulmonary function tests including forced vital capacity (FVC) and diffusing capacity for carbon monoxide (DLCO) in the valganciclovir treated group compared to placebo during active treatment and post-treatment follow-up. PFTs will be measured at baseline, 3 months (12 weeks), 6, 9 and 12 months after randomization to determine the FVC slope (change in FVC over time) and change in diffusion capacity (DLCO).

4.2.2. We will determine the effect of valganciclovir therapy on viral load in cell-free BAL fluid.

4.2.2.1. We will evaluate the change from baseline in daytime oxygen requirements. Oxygen requirements will be measured at study visits baseline, 3, 6, 9, 12 months. At each study visit, while at rest, the subject will be placed on the amount of supplemental O₂ required at the enrollment visit. After 5 minutes, the SpO₂ on this supplemental flow rate will then be recorded and evaluated in comparison to baseline. In addition, the patient will have his/her supplemental oxygen requirement determined to maintain oxygen saturation $\geq 88\%$ at rest. The change in liters per minute flow rate in oxygen compared to baseline will be recorded.

4.2.3. Exercise capacity will be determined on the basis of the 6 minute walk test (6MWT). The principal exercise capacity measurement will be the change in distance until SpO₂ reaches 80% compared to baseline. 6 MWT will be measured at study visits baseline, 3, 6, 9, 12 months. The 6MWT will be performed using a standardized protocol while the subject is breathing room air (i.e. without supplemental oxygen).

4.2.4. Additional secondary endpoints will analyze the immune response to herpesviruses by analyzing PD-1 expression by T lymphocytes and quantifying CMV- and EBV-antigen specific CD8⁺ T cell immune responses.

5. Background and Significance

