Randomization will be to pirfenidone plus placebo or pirfenidone plus valganciclovir. We prefer to have all subjects on pirfenidone as the standard of care for this study since the majority of patients elect to be treated with pirfenidone in our clinic. In addition, we anticipate valganciclovir will be better tolerated in combination with pirfenidone. We propose to enroll and randomize all eligible subjects with evidence of current or past EBV or CMV infection as determined by serologic testing for anti-EBV and CMV antibodies (total n=30) to treatment with pirfenidone plus valganciclovir (20 patients) or pirfenidone plus placebo (10 patients) for 12 weeks (**Fig. 1**). In order to maximize exposure to active treatment and assess for safety and tolerability, randomization will be 2:1 valganciclovir vs. placebo. The primary outcome will be safety and tolerability will be determined by type, frequency and duration of AE and SAEs. All study subjects will be offered bronchoscopy with BAL at study initiation and upon completion of treatment (12 weeks). Subjects will then be followed up at routine clinic visits at 6, 9 and 12 months for data collection.

[figure not shown]

Figure 1. Study flow chart.

6.2 **Rationale for Blinding and Placebo:**

6.1.1. A RCT is necessary given the clinical heterogeneity of IPF, and the inability to have two similar arms without randomization. A placebo arm will minimize bias since GI upset is a side effect of valganciclovir and standard treatment, pirfenidone. All subjects will be provided standard of care treatment to be applied equally across study groups as much as feasible and blinding will help avoid bias in the care provided.

6.1.2. Blinding is necessary to have optimal scientific validity, to make objective assessments of treatment effects, and to minimize dropout rates across study arms. In this study, there is particular concern that without blinding, subjects may opt to obtain off-label anti-viral therapy from non-study physicians if they become aware of the presence of herpesviruses in their lungs.

7. **Study population:** The study population will consist of male and female patients diagnosed with IPF, ages 21 and above, who are followed in the outpatient clinic setting.

7.1. **Inclusion criteria** will be:

- 7.1.1. age ≥ 21 and ≤ 80 years
- 7.1.2. ability to provided informed consent
- 7.1.3. diagnosis of probable or definite IPF according to ATS criteria(11)

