- 10.1. Screening visit: Once informed consent is obtained, subjects may begin the screening process. If a study subject has been evaluated at VUMC by a study physician and has performed clinical testing that meets study guidelines within 30 days, then this testing maybe used to qualify for study entry. This will facilitate entry into the study, avoid repeated testing, and reduce costs. The following procedures will be performed at screening: 1) medical history and physical examination; 2) vital signs including oximetry; 3) blood chemistries, hematology counts; EBV and CMV serology 4) PFTs including spirometry, lung volumes, and diffusing capacity; 5) HRCT review; 6) surgical lung biopsy review; and 7) recording of current medications. If patients are not taking pirfenidone at the time of screening, then patients will be placed on pirfenidone and will be re-assessed to determine study eligibility 4 weeks later to allow ample time to determine tolerance to pirfenidone.
- 10.2. Enrollment visit: For subjects who meet eligibility criteria, enrollment may occur the same day as the screening visit. For subjects who require blood tests to be drawn at the screening visit, they will be notified by telephone of their eligibility for the study and study drug will be mailed to subjects by the investigational drug pharmacy. Randomization will be 2:1 valganciclovir versus placebo. Subjects will be offered the opportunity to undergo an optional research bronchoscopy. For subjects who undergo bronchoscopy, study drug will begin immediately following the bronchoscopy. Subjects who do not undergo bronchoscopy will begin study drug immediately. Additional tests that will be obtained are the following: 1) six minute walk test (6 MWT); 2) baseline blood chemistries and blood counts if >30 days after the screening visit; 3) baseline blood draws for biomarker and immunology studies, including HLA-typing; 4) teaching subjects self-monitoring and diary recording; and 5) optional bronchoscopy with BAL. Bronchoscopy will be the last test performed at enrollment.

- 10.3. Week 4 and 8 study visits: The primary purpose of these visits is to establish safety of study treatment and adherence to study treatment. Subject's diaries will be reviewed, medical history and physical examination will be performed, a pill count will be performed, current medications will be recorded, and chemistries and hematology counts will be obtained.

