13.2. Sample Size and Randomization

- 13.2.1. Power analysis: This pilot study is designed to determine tolerability and safety of valganciclovir as add-on therapy to pirfenidone. Pirfenidone is reported to be discontinued in 13% of subjects due to adverse events, almost all of which occur within the first 4 weeks of treatment (based on AE profiles from the ASCEND study). Therefore, we do not expect any

placebo treated subjects to withdraw from this study. Using a 2:1 randomization (valganciclovir:placebo) and enrolling 30 subjects will allow us to detect an increased withdrawal rate in the valganciclovir group in the range of 25% (75% power with a one-sided $\alpha=0.1$). Subjects who require dose reduction, or temporary discontinuation but are able to resume treatment will be considered non-withdrawals.

13.2.2. **Randomization:** The randomization scheme will be a ratio of 2:1 for drug versus placebo. Once a participant has signed the consent form and completed the enrollment visit (and baseline bronchoscopy in subjects who participate in the bronchoscopy substudy), the participant will be randomized. Study medication will be distributed by the VUMC investigational pharmacy according to the randomization scheme.

13.3. **Statistical analysis:** For the primary endpoint, the rate-of-discontinuation of study drug due to adverse events will be compared between valganciclovir and placebo subjects by Chi-square. **Secondary analysis:** Frequencies of specific adverse event profiles will be compared between groups by Chi-square. This study is not powered to detect clinically significant changes in pulmonary function or perform multivariate analyses. Exploratory analyses for physiologic and biochemical endpoints will be performed using standard nonparametric statistics or paired tests when appropriate. The rate of change in FVC (cc/year) will be compared between valganciclovir therapy group (treatment group) compared to the standard of care (placebo) group. For other physiologic measurements (6MWD, oxygenation), similar analyses will be performed. For exploratory biomarker studies, paired analyses (Baseline vs. 12 weeks) will be performed comparing subjects randomized to valganciclovir or placebo. All analyses will be performed using STATA 11.0 (StataCorp, College Station, TX) and the programming language R (50).

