14.1 ASSESSMENT OF SAFETY

Specification of Safety Variables

Safety assessments will consist of monitoring and reporting adverse events (AEs) and serious adverse events (SAEs) that are considered related to {study drug}, all events of death, and any study specific issue of concern.

Adverse Events

An AE is any unfavorable and unintended sign, symptom, or disease temporally associated with the use of an investigational medicinal product (IMP) or other protocol-imposed intervention, regardless of attribution.

This includes the following:

- AEs not previously observed in the subject that emerge during the protocol-specified AE reporting period, including signs or symptoms associated with idiopathic pulmonary fibrosis that were not present prior to the AE reporting period.
- Complications that occur as a result of protocol-mandated interventions (e.g., invasive procedures such as cardiac catheterizations).

If applicable, AEs that occur prior to assignment of study treatment associated with medication washout, no treatment run-in, or other protocol-mandated intervention.

Preexisting medical conditions (other than the condition being studied) judged by the investigator to have worsened in severity or frequency or changed in character during the protocol-specified AE reporting period.

Serious Adverse Events

An AE should be classified as an SAE if the following criteria are met:

- It results in death (i.e., the AE actually causes or leads to death).
- It is life threatening (i.e., the AE, in the view of the investigator, places the subject at immediate risk of death. It does not include an AE that, had it occurred in a more severe form, might have caused death.).
- It requires or prolongs inpatient hospitalization.
- It results in persistent or significant disability/incapacity (i.e., the AE results in substantial disruption of the subject's ability to conduct normal life functions).
- It results in a congenital anomaly/birth defect in a neonate/infant born to a mother exposed to the IMP.
- It is considered a significant medical event by the investigator based on medical judgment (e.g., may jeopardize the subject or may require medical/surgical intervention to prevent one of the outcomes listed above).

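### Allocation is not stratified by bronchoscopy participation, so at low uptake the BAL endpoints could by chance be left with one placebo subject or none

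*Combined protocol and SAP*

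**What the plan says.** Section 13.2.2 is the plan's statement on allocation: "The randomization scheme will be a ratio of 2:1 for drug versus placebo". No stratification factor or block size is given there or elsewhere in the text available for review. Section 6.1 gives the arm sizes: "pirfenidone plus valganciclovir (20 patients) or pirfenidone plus placebo (10 patients) for 12 weeks".

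Section 13.2.2 also sets the order. The participant is randomised after consent and the enrolment visit ("and baseline bronchoscopy in subjects who participate in the bronchoscopy substudy"). Section 10.2 agrees in part: "Bronchoscopy will be the last test performed at enrollment". However, 10.2 mentions randomisation ahead of the bronchoscopy offer. Table 10.8 puts randomisation in the screening/enrolment column and bronchoscopy in a separate column.

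Bronchoscopy is optional. Section 3.2 says only "A subset of study subjects will undergo bronchoscopy with BAL at the time of study entry and at 12 weeks", with no target or minimum, overall or per arm. Section 4.2.2 makes BAL viral load a secondary endpoint: "We will determine the effect of valganciclovir therapy on viral load in cell-free BAL fluid". Section 11.2.2.3 adds assays on BAL lymphocytes. Section 13.3 plans baseline versus week 12 biomarker analyses that compare the arms.

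On safety, section 14.1 counts among adverse events "Complications that occur as a result of protocol-mandated interventions".

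**The concern.** The BAL endpoints can be measured only in subjects who choose bronchoscopy. That choice is known before allocation and cannot be affected by it, so it could be balanced at almost no cost. Without balancing, the number of placebo subjects in the subset is left to chance, and the placebo arm has only 10 subjects to draw on.

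At stake is the direct comparison of lung viral load between arms. Section 13.3 plans nonparametric tests. If the subset split 9 to 1, the single placebo value could take any of 10 ranks, so the smallest two-sided exact rank-sum p-value is 2/10 = 0.20. No viral-load effect, however large, could then be told from chance. Any loss of week 12 samples makes this worse.

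**Working it through.** **Inputs.** N = 30, with 20 valganciclovir and 10 placebo (section 6.1). Allocation is 2:1 with no stratification (13.2.2). The number opting for bronchoscopy, m, is not in the documents, so a range is assumed.

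**The plan's own figure.** The plan gives no figure for the substudy. Its only design calculation is 75% power for 25% versus 0% withdrawal at one-sided alpha 0.1 (13.2.1). A pooled normal approximation reproduces it:
- pooled rate = 5/30 = 0.1667
- null SE = √(0.1667 × 0.8333 × (1/20 + 1/10)) = 0.1443
- alternative SE = √(0.25 × 0.75/20) = 0.0968
- power = Φ((0.25 − 1.2816 × 0.1443)/0.0968) = Φ(0.67) = 74.9%

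This uses arm totals only, so the present point does not touch it.

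**Placebo subjects in the BAL subset.** With a fixed 20:10 split, the placebo count X among m participants is hypergeometric:

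P(X ≤ 1) = [C(20, m) + 10 × C(20, m−1)] / C(30, m)

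- m = 6: (38,760 + 155,040)/593,775 = 0.326
- m = 10: (184,756 + 1,679,600)/30,045,015 = 0.062

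If each subject were instead allocated independently, which the text does not exclude, X is Binomial(m, 1/3).

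| m (assumed) | P(X = 0), fixed split | P(X ≤ 1), fixed split | P(X ≤ 1), independent | Placebo count with stratified blocks of 3 |
|---|---|---|---|---|
| 6 | 6.5% | 32.6% | 35.1% | 2 |
| 8 | 2.2% | 15.4% | 19.5% | 2–3 |
| 10 | 0.6% | 6.2% | 10.4% | 3–4 |
| 12 | 0.2% | 2.1% | 5.4% | 4 |
| 15 | <0.1% | 0.3% | 1.9% | 5 |

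**Total under stratification.** With blocks of 3, each stratum's placebo count lies within one of a third of its size. At m = 10 the strata give 3–4 and 6–7, so the total is 9–11 placebo subjects against the planned 10. At m = 6, 12 or 15 it is exactly 10.

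**Share of each arm having bronchoscopy.** With k placebo participants, the shares are k/10 and (m − k)/20. The fixed-split chance that they differ by at least 30 points is 7.8% at m = 8, 10.1% at 10, 23.5% at 12, 11.9% at 13, 12.2% at 14, 24.5% at 15, 12.2% at 16 and 10.1% at 20. The jumps at 12 and 15 arise because a difference of exactly 30 points is attainable there and is counted. Neighbouring uptakes give 10–12%.

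**The case against.** Simple 2:1 allocation in a single-centre pilot of 30 is valid, and chance imbalance is not bias. Uptake is unknown and bronchoscopy is offered to everyone, so the subset may be large enough for the risk to vanish. Stratifying 6 participants still gives only 2 placebo subjects: the real limit is a small optional substudy. The plan treats these endpoints as exploratory and looks for trends. The text under the heading on randomization codes was not available, and 13.2.2 refers to a scheme held by the pharmacy, so stratification might be specified elsewhere. All of this stands. It sets the weight of the point but does not remove it, because the safeguard is nearly free.

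Two stronger readings are tempting.

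- A reader might infer that unequal bronchoscopy shares would distort the safety comparison. The documents give little support. Under 13.2.2 the baseline procedure precedes randomisation and study drug, and the second falls at week 12, when treatment ends. Discontinuation due to adverse events, the comparison in 13.3, should therefore barely move. Adverse events are recorded with dates and relationship to study drug (14.2), and no bronchoscopy complication rate is given from which to size a bias. What remains is a modest effect on raw event frequencies, which 4.1.1 names as the primary outcome.
- A reader might infer that the whole of Aim 2 is at risk. It is not: the peripheral-blood T-cell work is scheduled for all subjects. Only BAL viral load and BAL lymphocytes depend on the subset.

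**Conclusion.** The point holds as an inexpensive improvement for the BAL endpoints. With a fixed 20:10 split, the chance of 0 or 1 placebo BAL subjects runs from about 33% at 6 participants to 6% at 10, and is negligible by about 15. It is somewhat higher if subjects are allocated independently. These figures rest on assumed uptake, on participation being unrelated to allocation, and on no loss of week 12 samples. It would overstate the case to say that the BAL comparison will probably lack a placebo group: even at 10 participants the chance of none is 0.6%. The adverse-event aspect is secondary. A 30-point difference in bronchoscopy share has a chance of roughly 8–25% for uptakes of 8 to 20, and separate listing deals with it.

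**What to change.** Record each subject's bronchoscopy decision before allocation, and align section 10.2 and table 10.8 with 13.2.2 on this order. In 13.2.2, state that the pharmacy holds two blocked 2:1 lists, one for bronchoscopy participants and one for the rest. Blocks of 3 keep placebo BAL subjects within one of m/3, and block size should be withheld from study staff. If the pharmacy's scheme already does this, say so in 13.2.2.

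In the adverse event tables, list bronchoscopy complications separately from other events. No stratification is needed for that purpose alone.

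The cost is one additional list and a final split that may differ from 20:10 by about one subject. The change prevents an avoidable loss of placebo BAL data. It does not make a substudy of 6 to 10 participants informative, so the plan should also state the expected uptake.

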14. Safety and Adverse Events Monitoring: Study personnel will meet bi-weekly to review all safety laboratory data collected on each subject and review all adverse events. The study investigators will decide the appropriate steps to be taken to include dose modifications, and further monitoring. [name] will act as an on-site medical monitor who can become un-blinded to study drug if needed in order to adjudicate side effects are detected and whether they may due to valganciclovir. Planned safety analyses will occur after enrollment of 10 and 20 subjects by the medical monitor. If 5 more subjects have withdrawn from the study due to adverse events in the valganciclovir arm compared to placebo at either interim analysis, the study will be terminated.

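### Section 13.3 tests AE discontinuation in 20 vs 10 subjects by an unspecified chi-square; at one-sided 0.10 no chi-square version has the stated 75% power (exact power 90.9% uncorrected, 38.3% continuity-corrected)

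*Combined protocol and SAP*

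**What the plan says.** Section 6.1 plans "pirfenidone plus valganciclovir (20 patients) or pirfenidone plus placebo (10 patients) for 12 weeks". Section 13.2.1 does not expect any "placebo treated subjects to withdraw from this study". It says that 30 subjects suffice to detect an "increased withdrawal rate in the valganciclovir group in the range of 25% (75% power with a one-sided" alpha of 0.1).

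Section 13.3 then states that "the rate-of-discontinuation of study drug due to adverse events will be compared between valganciclovir and placebo subjects by Chi-square". It does not say whether a continuity correction or an exact version is meant, and it does not repeat or refer to the one-sided 0.10. On software it says only that "All analyses will be performed using STATA 11.0 (StataCorp, College Station, TX) and the programming language R". The secondary safety analysis has the same form: "Frequencies of specific adverse event profiles will be compared between groups by Chi-square".

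The only rule that acts on discontinuations is the count in section 14, which ends the trial on this condition: "If 5 more subjects have withdrawn from the study due to adverse events in the valganciclovir arm compared to placebo at either interim analysis".

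**The concern.** Several tests go by the name chi-square, and in samples of 20 and 10 they do not agree. With about 5 events in total, one event more or fewer in the rejection threshold moves the power a long way, and the threshold depends on whether a continuity correction is applied.

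This is the only comparison for which the plan states a power. If the version is left open, two analysts following section 13.3 could report opposite conclusions from the same data, and the choice could be made after the data are seen. The power in section 13.2.1 would also describe neither analysis.

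**Working it through.** **Inputs.** n1 = 20 and n0 = 10 (section 6.1). Rates of 25% vs 0% and one-sided alpha 0.10 (section 13.2.1). The plan says the detectable rate is in the range of 25%; exactly 25% is used here.

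**Expected counts.** 20 × 0.25 + 10 × 0 = 5 events in 30. Under no difference these split as 20 × 5/30 = 3.33 and 10 × 5/30 = 1.67, both below 5.

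**Reproducing the 75%.** Pooled rate 5/30 = 0.1667.
- Null standard error: √(0.1667 × 0.8333 × (1/20 + 1/10)) = 0.1443.
- Standard error under the alternative: √(0.25 × 0.75/20) = 0.0968.
- Power ≈ Φ[(0.25 − 1.2816 × 0.1443)/0.0968] = Φ(0.672) = 74.9%.

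Subtracting the continuity correction 0.5 × (1/20 + 1/10) = 0.075 from the difference gives 45.9%. The stated figure therefore matches the uncorrected pooled approximation.

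**Exact rejection thresholds with no placebo events, one-sided 0.10.**
- Uncorrected: 3 vs 0 gives z = 0.15/√(0.1 × 0.9 × 0.15) = 1.291, p = 0.0984, rejected. 2 vs 0 gives p = 0.150, not rejected.
- Continuity-corrected: 5 vs 0 gives p = 0.113, not rejected. 6 vs 0 gives p = 0.073, rejected.

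**Exact power and size.** All 21 × 11 = 231 outcomes were enumerated and binomial probabilities summed. With a placebo rate of 0%, power is P(X ≥ threshold) for X ~ Binomial(20, 0.25). The 30% vs 5% column is an assumed scenario, to show the effect of a few placebo withdrawals. Size is the rejection probability when both arms share one rate.

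| One-sided test, 0.10 | Rejects from | Power 25% vs 0% | Power 30% vs 5% | Maximum size, any common rate |
|---|---|---|---|---|
| Uncorrected chi-square | 3 vs 0 | 90.9% | 71.0% | 18.2% |
| Continuity-corrected chi-square | 6 vs 0 | 38.3% | 38.6% | 5.7% |
| Ordinary Fisher | 6 vs 0 | 38.3% | 42.3% | 5.0% |
| Barnard (pooled z) | 4 vs 0 | 77.5% | 66.2% | 8.8% |

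The uncorrected test's size is 0.6% at a common rate of 2%, 4.5% at 5%, 11.4% at 10% and 12.6% at 13%. It passes 10% at a common rate of about 8.7%. Its peak is 12.6% for rates up to 50%; the 18.2% arises near a common rate of 93%.

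**The design outcome, 5/20 vs 0/10.** Uncorrected: z = 0.25/0.1443 = 1.732, one-sided p = 0.042. Corrected: z = (0.25 − 0.075)/0.1443 = 1.21, one-sided p = 0.113. The first is below 0.10 and the second is not.

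**Other splits.** Fisher mid-p rejects the same outcomes as Barnard at 20/10. At 21/9 the two differ on 5 outcomes and mid-p has size 10.5%; at 18/12 they differ on 3 and mid-p has size 10.6%. At 20/9 Barnard rejects from 5 vs 0 and its power for 25% vs 0% is 58.5%.

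**The case against.** **The plan does give a side and a level.** Section 13.2.1 states one-sided 0.10 for this same comparison, and no other level appears. This stands. A reader might infer that a two-sided test at 0.10 or 0.05 is equally open (exact power 58.5% and 21.4% uncorrected), but that would depart from the only level stated. The gap is a missing cross-reference and an unnamed version, and at one-sided 0.10 the version alone moves power from 90.9% to 38.3%.

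**The 75% might come from an exact-type calculation.** The plan says only in the range of 25%, and a test rejecting from 4 vs 0 has 74.3% power at 24%. This is possible. The uncorrected approximation is the closest match at 25%, not a proven source. But a test with that threshold is not a chi-square version at 20/10, so section 13.3 would still name something else.

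**More power than stated does no harm.** In part. The 90.9% needs exactly 0% on placebo and exactly 20/10. It falls to 71.0% at 30% vs 5%, and at 20/9 the uncorrected test rejects only from 4 vs 0, with 77.5% power.

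**Type I error is not a problem where the plan operates.** At the near-zero rates it expects, the uncorrected test's size is below 10%. The excess matters only if discontinuation is commoner. Section 13.2.1 cites 13% AE discontinuation on pirfenidone, but as mostly early, and uses that to argue for none here.

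**This is a pilot.** Sections 4.1.1 and 6.1 describe the primary outcome as AE type, frequency and duration, and no decision is tied to the p-value. This stands and limits the consequence to reporting.

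**Conclusion.** The point holds in limited form. Section 13.3 leaves open which chi-square is meant, and at one-sided 0.10 neither the uncorrected nor the continuity-corrected test has the stated power for 25% vs 0%. The design outcome is significant under one and not under the other. This should be fixed before unblinding. It affects how the primary result is read and reported, not whether the trial continues.

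Three stronger readings are not supported. The 75% is not an arithmetic error, since it reproduces. The trial does not in truth have 90.9% power, since that figure is specific to one version, a 0% placebo rate and a 20/10 split. The uncorrected test does not exceed its level at the rates the plan expects, only above a common rate of about 8.7%.

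The figures assume a 20/10 split, complete follow-up and independent binomial counts, and they ignore the interim rule in section 14.

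**What to change.** **Section 13.3.** Name one test: a one-sided unconditional exact test (Barnard, pooled z statistic) at 0.10, computed for the arm sizes actually realised. Report the difference in discontinuation rates with an exact confidence interval of stated level.

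Do not write only that an exact test will be used, because ordinary Fisher has 38% power. Do not treat Fisher mid-p as interchangeable: it coincides with Barnard at 20/10 but can exceed 0.10 at other splits.

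**Section 13.2.1.** Restate the exact power of that test at 20/10 as about 77% for 25% vs 0% and about 66% for an assumed 30% vs 5%, with size at most 8.8% at any common rate. Note that power depends on the realised split (58.5% at 20/9 for 25% vs 0%) and that the figures ignore the interim stopping rule.

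**AE frequencies.** Use exact tests where events are sparse. The expected placebo count is 10 × m/30 for m subjects with the event, so it is below 5 whenever m is under 15.

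**Cost.** Wording only, with no extra subjects, visits or data. The statistical price, against the uncorrected one-sided test, is that the cut-off with no placebo events moves from 3 to 4 and power for 25% vs 0% falls from 90.9% to 77.5%. Because the endpoint is a harm, that loss of sensitivity should be accepted openly.
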